5.11.3 Efficacy Criteria for Stopping Enrollment

- If a total of ≥ 2 out of the first 10 HIV-infected subjects in the PP population across all arms experience confirmed loss of HIV-1 virologic suppression, then no additional HIV/HCV co-infected subjects will be enrolled. Loss of virologic suppression is defined as HIV-1 RNA ≥ 200 copies/mL, confirmed on 2 consecutive tests at least 2 weeks apart in subjects compliant with their HIV ARV therapies. Remaining co-infected subjects who are already on trial treatment would continue HCV treatment regimen while their HIV regimen is being reassessed.
- If a total of ≥ 3 out of the first 10 subjects in the PP population enrolled in a 12-week dosing duration arm experience virologic non-response, rebound, breakthrough or relapse by FW4, no further subjects will be enrolled in that 12-week treatment arm.

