8.5 Analysis Populations

8.5.1 Efficacy Analysis Populations

Per Protocol (PP)

The PP population will serve as the primary population for the analysis of SVR₁₂ and SVR₂₄ in this study, since it provides a more accurate assessment of the virological efficacy in subjects who are reasonably compliant in this Phase 2 trial. The PP population excludes subjects due to important deviations from the protocol that may substantially affect the results of the primary and secondary efficacy endpoints. Non-virologic failures that are due to administrative reasons will be excluded. Potential violations that may result in the exclusion of a patient from the PP population include:

- The subject did not meet specific inclusion/exclusion criteria (for example, the subject is infected with a mixed GT infection or non-typeable genotype).
- The subject received concomitant medications that are prohibited due to their potential to result in a clinically significant lowering of the MK-3682 or MK-8408 concentrations (see Section 5.5 for specific details of prohibited medications). Further, any co-administered medication currently unidentified, but for which subsequent clinical DDI data indicate that co-administration with MKs leads to a clinically significant lowering of MK concentrations.
- Other violations may be identified during the course of data collection and they will be listed specifically in the CSR.

A subject with important deviations from the protocol at treatment allocation (Day 1) will be excluded from the PP population. For subjects with important deviations from the protocol as described above during the course of treatment, data obtained subsequent to the violation will be excluded from analysis.

Full Analysis Set (FAS)

The FAS population will serve as a supportive analysis of efficacy data in this study. The FAS population consists of all subjects who are assigned to a treatment arm and receive at least one dose of study treatment in this study.

Modified Full Analysis Set (mFAS)

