The mFAS population will be used for the efficacy endpoints of SVR₁₂ and SVR₂₄ as a supportive analysis and for the endpoint of the proportion of subjects experiencing virologic failure at FW12 as a primary analysis. The mFAS population is a subset of the FAS population, with subjects excluded for study discontinuation for reasons unrelated to the treatment regimen. Examples include loss to follow-up, discontinuation from the study due to non-drug related AEs, informed consent withdrawal, and other non-virologic failures.

The final determination on the exclusion of subjects from various analysis populations will be made prior to the final database lock and will be documented in a separate memo.

Subjects will be included in the treatment arm to which they are allocated for the analysis of efficacy data using the FAS, mFAS, and PP populations. Details on the approach to handling missing data are provided in Section 8.6, Statistical Methods.

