8.6.1 Statistical Methods for Efficacy Analyses

Missing Values

A missing data point for a given study visit may be due to any one of the following reasons: a visit occurred but data were not collected or were unusable; a visit did not occur; or a subject discontinued from the study before reaching the visit. Subjects who prematurely discontinued the assigned treatment are encouraged to remain in the study for follow-up, if possible.

The HCV RNA outcome is categorized as TND, TD (u), and TD (q). There are 3 types of missing data handled by different approaches.

1. Intermittent missing: If a missing data point is immediately preceded and followed by non-missing HCV RNA outcomes, the missing value would be imputed to the worst outcome of the two. For example, if a missing data point is preceded by TD(q) and followed by TD(u) or TND, then the missing value would be imputed as TD(q); if a missing data point is preceded by TD(u) and followed by TND, then the missing value would be imputed as TD(u); when a missing value is flanked by two TND, then the missing value would be imputed as TND.

2. Non-intermittent missing related to the study drug: For missing values due to premature study discontinuations due to treatment related reasons either for safety or efficacy, the missing values will be considered as treatment failures.
3. Non-intermittent missing for reasons unrelated to the study drug: For missing data due to premature study discontinuations with reasons unrelated to treatment such as loss to follow-up, protocol deviation, withdrawal of consent, administrative reasons, etc., the missingness mechanism is unlikely to be related to subjects' response to the HCV treatment, and therefore the missing at random (MAR) assumption is reasonable.

The following two approaches will be used to handle non-intermittent missing data due to premature discontinuations, depending on the analytical strategy, as described in the section below and in [Table 15](#).

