1. Treatment-Related Discontinuation = Failure (TRD=F) approach: Subjects with treatment-related missing data (type #2 above) will be considered as failure; whereas the subjects who have the non-treatment-related missing value (type #3 above) and who do not have virologic failure during the observed study period will be excluded from the analysis for the time points following their study withdrawal. Note that subjects with documented virologic failure during the treatment or follow-up period, even if they withdrew prematurely due to reasons not related to study drug, are classified as failures.
2. Missing=Failure (M=F) approach: Subjects with any non-intermittent missing data (i.e., type #2 and #3 above) will be imputed as failures, regardless of the reason for study discontinuation.

In addition, a missing baseline/Day 1 HCV RNA result will be replaced with a screening result, if available.

Proportions of Subjects With Virologic Responses and Virologic Failures

For the primary efficacy analysis, the proportions of subjects achieving SVR₁₂ after 12 weeks of treatment in each treatment arm will be provided and 95% confidence intervals for these rates will be calculated using the Clopper-Pearson method [49]. The same method will be used to analyze all binary endpoints including SVR₂₄ after 12 weeks of treatment.

For all analyses conducted using the PP and mFAS populations, the missing data approach of TRD=F will be utilized. In addition, for all analyses in these two populations, a subject will be considered to have achieved a particular endpoint if the HCV RNA levels for the infection he/she had at baseline are < LLOQ. In other words, if a subject has HCV RNA levels \geq LLOQ at a particular time point, but those RNA levels correspond to an infection that is of a different genotype and/or subtype compared to the infection detected at baseline and the baseline infection has been cleared, then the subject is considered to have achieved response for the given endpoint.

Sensitivity analyses that use the FAS population will utilize the M=F missing data approach. Also, in the FAS analyses, only subjects with HCV RNA levels < LLOQ for any type of HCV infection at a given time point will be considered to have achieved the endpoint.

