PP (Primary for SVR ₁₂ and SVR ₂₄)	HCV RNA < LLOQ for baseline infection HCV RNA ≥ LLOQ demonstrated to be due to reinfection (after clearance of baseline infection)	HCV RNA ≥ LLOQ for baseline infection*	Subject with important deviations from the protocol including subject discontinued from the study for non-treatment related reasons and other violations such as violation of I/E criteria, use of prohibited concomitant medications (see Section 8.5.1)
mFAS (Supportive for SVR ₁₂ , SVR ₂₄ ; Primary for proportion of subjects experiencing virologic failure at FW12)	HCV RNA < LLOQ for baseline infection HCV RNA ≥ LLOQ demonstrated to be due to reinfection (after clearance of baseline infection)	HCV RNA ≥ LLOQ for baseline infection*	Subject discontinued from the study for non-treatment related reasons.
FAS (Supportive for SVR ₁₂ and SVR ₂₄)	HCV RNA < LLOQ	HCV RNA ≥ LLOQ	Subject did not receive at least one dose of study medication
mFAS = modified Full Analysis Set FAS = Full Analysis Set PP = Per Protocol LLOQ = Lower limit of quantification *Baseline infection: Genotype(s) and subtype(s) present at baseline based on population sequencing and genotyping assay			

Subject Virologic Failure: Non-response, Rebound, Virologic Breakthrough, Relapse and Reinfection

Summary statistics will be provided to describe the rates of occurrence of subject non-response, rebound, virologic breakthrough, and relapse. Definitions for subject non-response, rebound, virologic breakthrough, and relapse are in Section 4.2.3.1.1.2. Reinfection will be defined as having detectable virus of a different genotype than that detected at baseline as determined by sequencing. Those with reinfection will be considered treatment success in the mFAS and PP analyses as long as the baseline infection was achieved HCV RNA < LLOQ.

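### The HIV enrolment-stopping rule in 5.11.3 counts a harm signal in a provisional, HCV-oriented per-protocol population that also admits subjects not on ART

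*Combined protocol and SAP*

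**What the plan says.** Section 5.11.3 closes enrolment to co-infected subjects if a total of at least 2 "out of the first 10 HIV-infected subjects in the PP population across all arms experience confirmed loss of HIV-1 virologic suppression". An event is HIV-1 RNA of 200 copies/mL or more, confirmed on a further test no sooner than 2 weeks later, in a subject who adheres to ART. Co-infected subjects already on treatment carry on.

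Section 8.5.1 makes PP the primary population for SVR12 and SVR24. Its exclusions target deviations that could distort the primary and secondary efficacy endpoints, which 8.4.1.1 defines entirely by HCV outcomes. Three features matter here:

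- Deviations at entry remove the person: "A subject with important deviations from the protocol at treatment allocation (Day 1) will be excluded from the PP population".
- For deviations during treatment, only "data obtained subsequent to the violation will be excluded from analysis".
- The list is open and settled late: "Other violations may be identified during the course of data collection", and "The final determination on the exclusion of subjects from various analysis populations will be made prior to the final database lock".

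Section 8.6.1 deals with exits. Its examples of unrelated reasons are "premature study discontinuations with reasons unrelated to treatment such as loss to follow-up, protocol deviation, withdrawal of consent, administrative reasons". Under the TRD=F approach such subjects, if they had no virologic failure, "will be excluded from the analysis for the time points following their study withdrawal". Table 16 gives the PP exclusion as "Subject with important deviations from the protocol including subject discontinued from the study for non-treatment related reasons", with a pointer to 8.5.1.

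The note under Table 10 (5.8) lets a subject with HIV failure stay in the study unless the new HIV regimen needs a prohibited drug. Criterion 11a admits subjects who take no ART. Criterion 11b covers those with controlled HIV on ART.

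**The concern.** Loss of HIV suppression harms the subject, whatever the heading of 5.11.3 says. The other harm-based enrolment rules (5.11.1, 5.11.2) are not restricted to PP, safety is analysed in all treated subjects (8.5.2), and HIV failure is an exploratory endpoint with no PP restriction stated (8.4.1.3). Only this rule passes a harm through exclusions designed for HCV efficacy.

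Two things follow. First, who the ten are can only be a working judgement while enrolment is open, and the plan gives no provisional PP definition. Second, the exclusions may depend on the event: HIV failure can force a regimen that ends study participation, and no text says how that exit is classed. Section 8.6.1 keeps documented virologic failures as failures whatever the reason for withdrawal, but the term there refers to HCV. No such safeguard is written for HIV.

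Separately, a subject not on ART takes one of the ten places but is not naturally able to produce an event defined by loss of suppression in someone adhering to ART.

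At stake is a missed stop. Co-infected enrolment has no cap (2.1), so it could continue after two real events.

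**Working it through.** **1. The plan's own figures.** The documents state no firing probability for the HIV rule. The nearest figures are in Table 18 (8.7), for at least 3 HCV failures. With X ~ Binomial(n, 1 − SVR), P(X ≥ 3) at SVR 0.80 is 0.2618 for n = 9 and 0.3222 for n = 10, against 26.2% and 32.2% printed. All twelve entries reproduce, so the same exact binomial is used below.

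**2. The HIV rule with fewer effective places.** Let p be the true loss rate, which is an assumption because the documents give none. Then P(X ≥ 2) = 1 − (1−p)^n − n·p·(1−p)^(n−1). For p = 0.20 and n = 10: 1 − 0.1074 − 0.2684 = 0.6242.

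| p (assumed) | n = 10 | n = 9 | n = 8 |
|---|---|---|---|
| 10% | 26.4% | 22.5% | 18.7% |
| 20% | 62.4% | 56.4% | 49.7% |
| 30% | 85.1% | 80.4% | 74.5% |

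*Entry deviations unrelated to HIV.* The plan assumes 10% violations, leaving about 9 of the first ten (4.2.1.3, for the HCV rule). Without replacement, n = 10 becomes n = 9: falls of 3.9, 6.0 and 4.7 points. If the next PP subject takes the place, n stays at 10 and nothing changes.

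*Subjects not on ART.* If they cannot produce an event, one such subject among the ten gives the n = 9 column and two give n = 8. How many would enrol is not stated.

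**3. Which events survive the text.**

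- Confirmed event, then ART switch: kept, because 8.5.1 drops only later data.
- First raised test, then a switch to a prohibited drug that lowers study-drug levels, then the confirming test: the second test falls after the violation and could be dropped. The documents do not say which HIV drugs lower those levels.
- Confirmed event, then an exit classed as unrelated to treatment: kept if the time-point rule of 8.6.1 governs, removed if Table 16 is read as excluding the whole subject.

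**4. Event-linked removal.** Let d be the assumed share of event subjects removed. With replacement, the rate among those counted is q = p(1−d)/(1−pd). Without replacement, q = p(1−d). In both cases n = 10.

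| p | d | replaced | not replaced |
|---|---|---|---|
| 10% | 10% | 22.9% | 22.5% |
| 10% | 25% | 17.7% | 17.0% |
| 20% | 10% | 57.3% | 56.1% |
| 20% | 25% | 48.4% | 45.6% |

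**5. Sensitivity to a single removal.** Exactly two events make up 0.1937/0.2639 = 73% of firings at p = 10% and 0.3020/0.6242 = 48% at p = 20%. Given exactly two events and one removed before the rule fires, the trigger is lost if there is no replacement. With one replacement it is lost with probability 1 − p, which is 90% or 80%. These are conditional figures and do not say how often a removal happens.

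**The case against.** The strongest reply is that no effect is demonstrated. Every loss rate and removal share is assumed. The rule's wording most naturally means ten PP subjects, so an entry exclusion is simply replaced and the probability is unchanged. Confirmation normally comes before a switch: 7.1.3.4 draws the HIV resistance sample at the confirmation visit, and 5.8 speaks of a new regimen after failure. Table 16 refers back to 8.5.1, and most Table 10 scenarios stop treatment but keep the subject under observation. Provisional PP membership is also how the HCV rules in 5.11.3 and 5.12.1 work, in an open-label trial that the sponsor reviews throughout (8.2).

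Most of this stands, and it limits the size of the point. It does not answer why a harm count should depend on HCV exclusions at all, or how an exit after HIV failure is to be classed. Nor does it touch the places taken by subjects not on ART.

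The reply also bears on the remedy. Counting everyone suppressed on ART at baseline would admit subjects who breach the 8-week suppression, 4-week stability or permitted-drug conditions of criterion 11b, and protecting events after any ART change would count rebounds caused by an unrelated switch. The fix below avoids both.

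**Conclusion.** The point holds as a cheap improvement. The rule uses a population designed for another purpose, provisional when it is needed, with an unresolved route for event-linked removal and with places open to subjects outside the rule's intent. The size is unknown and possibly small. At assumed loss rates of 10% to 30%, random exclusion costs about 4 to 6 points without replacement and nothing with it. Event-linked removal costs more (62.4% to 48.4% or 45.6% at a 20% loss rate if a quarter of event subjects are removed), but requires an exit classed as unrelated or an ART switch between the two tests.

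A reader might infer more, and the documents do not support it:

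- That any ART switch after HIV failure erases the event. Section 8.5.1 drops only later data.
- That the rule cannot be run before database lock. Nothing forbids working decisions on membership; they are merely undefined.
- That co-infected subjects go unmonitored if the rule fails to fire. HIV RNA testing, individual HIV care and sponsor review continue, so the consequence is limited to further co-infected enrolment. An exclusion made after enrolment has stopped changes nothing.

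**What to change.** In the HIV rule of 5.11.3, replace the PP restriction with: *the first 10 HIV co-infected subjects who met criterion 11b (suppressed at screening on a stable, permitted ART regimen) and received at least one dose of study treatment*. Add one sentence: *A confirmed event whose first HIV-1 RNA of 200 copies/mL or more came before any ART change or study exit stays in the count.* Keep the threshold of 2, the confirmation requirement and the ART-adherence condition, which is already part of the event definition and so is not lost by leaving PP.

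Membership is then known at first dose, and subjects not on ART no longer fill places. The change needs one phrase, one sentence and no new data. The cost is that subjects with HCV-only deviations count, so the rule is slightly more likely to fire. It cannot recover an event whose confirming test is never drawn.

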2.0 TRIAL DESIGN

2.1 Trial Design

This study will evaluate a novel two-drug combination regimen to treat hepatitis C virus (HCV) infection of all genotypes (GTs). This is an open-label, multi-center trial in subjects with chronic HCV GT1, GT2, GT3, GT4, GT5 or GT6 infection. All subjects in this study will receive the same treatment regimen that consists of MK-3682 (450mg) + MK-8408 (60mg) co-administered concomitantly as separate medications once daily for 12 weeks. An estimated total of 250 subjects will be enrolled, with an overall target enrollment in six arms of 50 GT1, 50 GT2-, 50 GT3-, approximately 50 GT4-, approximately 25 GT5-, and approximately 25 GT6-infected subjects as displayed in Table 1. Subjects who have prior treatment experience with interferon (IFN)-based therapy may be enrolled, but subjects may not have previously received treatment with HCV direct-acting antiviral (DAA) therapy. Subjects may be HCV mono-infected or HCV/HIV-co-infected. HCV/HIV co-infected subjects and IFN-treatment-experienced subjects may be enrolled with no minimum number or caps.

Table 1 Treatment Regimen and Subject Characteristics

Treatment Regimen	Treatment Arm	Group Characteristics (N = 250)		
		Genotype (GT)	Target Enrollment	Target Cirrhotics
MK-3682 450 mg + MK-8408 60 mg for 12 weeks	1	GT1a	n = 35	n ~10
		GT1b	n = 15	n ~ 5
	2	GT2	n = 50	n ~15
	3	GT3	n = 50	n ~15
	4	GT4	n ~ 50	n ~15
	5	GT5	n ~ 25	N/A
6	GT6	n ~ 25	N/A	

If a total of ≥ 3 out of the first 10 subjects in the per-protocol (PP) population of the 12-week treatment arm experience virologic relapse by Follow-up Week 4 (FW4), the treatment duration of any remaining subjects of that genotype still on treatment in the 12-week arms will be extended to 16 weeks.

All subjects will be followed for 24 weeks after the end of treatment. Any subject who has taken at least one dose of study drug (either MK-3682 or MK-8408), experiences virologic failure, AND completes Follow-up Week (FW) 24 will be asked to extend follow-up for a total of 3 years after the end of treatment.

Amendment 04 implemented the discontinuation of the LTFU period of the trial. Subjects who already entered the LTFU period are to be discontinued (via an unscheduled visit). No further subjects will be entered into the LTFU period.

Safety and tolerability will be carefully monitored throughout the study by the Sponsor in accordance with standard procedures.

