[†]Abstinence (relative to heterosexual activity) can be used as the sole method of contraception if it is consistently employed as the subject's preferred and usual lifestyle and if considered acceptable by local regulatory agencies and ERCs/IRBs. Periodic abstinence (e.g., calendar, ovulation, sympto-thermal, post-ovulation methods, etc.) and withdrawal are not acceptable methods of contraception.

[‡]If a contraceptive method listed above is restricted by local regulations/guidelines, then it does not qualify as an acceptable method of contraception for subjects participating at sites in this country/region.

8. understand the study procedures, alternative treatments available, risks involved with the study, and voluntarily agrees to participate by giving written informed consent.
9. provide written informed consent for the trial. The subject may also provide consent for Future Biomedical Research. However, the subject may participate in the main trial without participating in Future Biomedical Research.

For HIV co-infected subjects these additional criteria must also be met:

10. have HIV-1 infection documented by any licensed rapid HIV test or HIV enzyme or chemiluminescence immunoassay (E/CIA) test kit at any time prior to study entry

(Day 1) and confirmed by a licensed Western blot or a second antibody test by a method other than the initial rapid HIV and/or E/CIA, or by HIV-1 p24 antigen, or plasma HIV-1 RNA VL.

11. meet one of the following criteria:

- a. not currently be on antiretroviral therapy (ART) and have no plans to initiate ART treatment while participating in this study.
 - i. subjects not on ART must have CD4+ T-cell count >500 cells/mm³ at time of screening
- b. have well controlled HIV on ART, defined as:
 - i. subjects on ART must have a CD4+ T-cell count >200 cells/mm³ at time of screening
 - ii. subjects on ART must have achieved and maintained virologic suppression (defined as confirmed HIV RNA level below the LLOQ of available assay at the time of screening) for at least 8 weeks prior to screening
 - iii. subjects on ART must have been on a stable regimen, without changes in drugs or dose modification, for at least 4 weeks prior to study entry (Day 1)
 - iv. the combination ART regimen must not contain any antiretroviral medications other than: tenofovir, abacavir, lamivudine, emtricitabine, raltegravir, dolutegravir or rilpivirine

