The subject's ALT or AST increases to >3x nadir, is >3x ULN (confirmed with repeat test within one week), and is temporally associated with signs or symptoms of liver inflammation that are of moderate or severe intensity and deemed by the investigator to be at least possibly related to study therapy.	Discontinue from Treatment (should continue to monitor in the trial)
The subject's serum creatinine increases to Grade 3 or higher (>1.8x upper limit of normal), confirmed with repeat test within one week.	Discontinue from Treatment (should continue to monitor in the trial)
The subject's creatinine clearance (eGFR) decreases to <30 mL/min/1.73 m ² , confirmed with repeat test within 1 week. Creatinine clearance will be evaluated as an estimated GFR (eGFR), based on the modification of diet in renal disease (MDRD) equation: $eGFR \text{ (mL/min/1.73 m}^2\text{)} = 175 \times (\text{Scr, std})^{-1.154} \times (\text{Age})^{-0.203} \times (0.742 \text{ if female}) \times (1.212 \text{ if black})$ Scr, std: serum creatinine measured with a standardized assay	Discontinue from Treatment (should continue to monitor in the trial)
The subject has a Grade 4 laboratory AE, or a life-threatening clinical AE, or an AE that results in or prolongs an existing in-subject hospitalization, that is assessed to be a study drug-related laboratory or clinical AE.	Discontinue from Treatment (should continue to monitor in the trial)
SAE assessed by the physician investigator as possibly or probably related to study medication. Investigator may continue the subject in the trial, if it is deemed to be in the best interest of the subject to stay on the study treatment after consultation with Sponsor.	May Discontinue from Treatment (should continue to monitor in the trial)
Failure to comply with the dosing, evaluations, or other requirements of the trial.	May Discontinue from Treatment (should continue to monitor in the trial)

NOTE: Clinical management of HIV-1 virologic failure will be handled by site investigators according to current HIV treatment guidelines and local standard of care. Subjects with HIV virologic failure may continue in the study unless there is a requirement for prohibited concomitant medications (see Section 5.5) to construct a new HIV treatment regimen.

Discontinuation from treatment is “permanent.” Once a subject is discontinued, he/she shall not be allowed to restart treatment.

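### The HIV stopping rule in Section 5.11.3 counts the first 10 HIV-infected per-protocol subjects whether or not they take ART, but its event can occur only in subjects on ART, so off-ART subjects among the ten weaken it

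*Combined protocol and SAP*

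**What the plan says.** **The rule (5.11.3).** Enrolment of co-infected subjects stops if at least two of the first ten "HIV-infected subjects in the PP population across all arms experience confirmed loss of HIV-1 virologic suppression". The event is HIV-1 RNA of 200 copies/mL or more, "confirmed on 2 consecutive tests at least 2 weeks apart in subjects compliant with their HIV ARV therapies". Co-infected subjects already on trial treatment "would continue HCV treatment regimen while their HIV regimen is being reassessed". Section 7.1.3.4 repeats the ART-compliance condition when it defines potential HIV failure.

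**Who can be among the ten (5.1.2, criterion 11).** There are two routes of entry for HIV co-infected subjects. Under 11a a subject must "not currently be on antiretroviral therapy (ART) and have no plans to initiate ART treatment while participating in this study", and needs a CD4+ count above 500 cells/mm³; no HIV RNA level is required. Under 11b, "subjects on ART must have achieved and maintained virologic suppression".

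**What might narrow the ten.** Section 8.5.1 says: "The PP population excludes subjects due to important deviations from the protocol". Entry under 11a is permitted, so it is not a deviation. Section 2.1 says: "HCV/HIV co-infected subjects and IFN-treatment-experienced subjects may be enrolled with no minimum number or caps". It gives no split by ART status.

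**The concern.** The numerator and denominator of the rule refer to different groups. Loss of suppression in a subject compliant with ARV therapy presupposes both suppression at entry and a regimen to comply with. A subject who enters under 11a and stays off ART need have neither, but is HIV-infected and per-protocol and so fills one of the ten places.

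If the rule is followed as written, each such subject reduces the number who can contribute an event while the threshold stays at two. The rule is then less likely to halt co-infected enrolment if the regimen does disturb HIV control. It is the only group-level HIV criterion in the plan: Sections 5.11.1, 5.11.2 and 5.12.1 contain none, and the interim assessment in 8.7 concerns HCV relapse.

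**Working it through.** **Inputs**
- Threshold: 2 events among the first 10 (5.11.3).
- k, the number of the ten who stay off ART: not in the documents; assumed 0, 1 or 3.
- p, the probability of confirmed loss for a subject on ART: not in the documents; assumed 5%, 10% or 20%.

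**Check of method.** The plan states no operating characteristics for the HIV rule, so there is no figure of its own to reproduce. It does give them for the HCV rule (Table 18, Section 8.7: three or more failures among 9 or 10). The exact binomial tail reproduces all 12 cells of that table to rounding; for example, 5.3% for n = 9 and 7.0% for n = 10 at a true SVR of 0.90.

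**Formula.** With n = 10 − k subjects at risk,

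P(fires) = 1 − (1 − p)^n − n·p·(1 − p)^(n−1).

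**Worked case, p = 10%**
- k = 0: 1 − 0.9^10 − 10(0.1)(0.9^9) = 1 − 0.3487 − 0.3874 = 26.4%.
- k = 1: 1 − 0.9^9 − 9(0.1)(0.9^8) = 1 − 0.3874 − 0.3874 = 22.5%.

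**Results: chance that the rule fires**

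| True loss p | k = 0 | k = 1 | k = 3 |
|---|---|---|---|
| 5% | 8.6% | 7.1% | 4.4% |
| 10% | 26.4% | 22.5% | 15.0% |
| 20% | 62.4% | 56.4% | 42.3% |

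One off-ART subject costs 3.9 points at 10% loss and 6.0 points at 20%. The loss rate at which the rule fires half the time rises from 16.2% (k = 0) to 18.0% (k = 1) and 22.8% (k = 3). With nine or more off ART the rule cannot fire.

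**When restricting the ten would change anything.** The restricted ten contain every on-ART subject in the current ten, plus later on-ART subjects who take the vacated places. Two things follow:
- On the same data the restricted rule never fires later than the current one.
- If ten or fewer HIV-infected per-protocol subjects are enrolled in total, no later subjects exist. Both rules then count the same people and the same events, and P(fires) is identical.

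The k = 0 column is therefore reached only if at least k further on-ART co-infected per-protocol subjects are enrolled after the tenth. If three of the ten are off ART and only one more on-ART subject follows, n goes from 7 to 8, and at p = 10% the chance goes from 15.0% to 18.7%, not to 26.4%.

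**The case against.** The best answer is that the rule already means subjects on ART. It speaks of loss of suppression, of compliance with ARV therapies and of a regimen under reassessment, and only 11b subjects had to be suppressed at entry. That reading is natural, and a study team might well apply it. But the words that define the ten do not say so, and a stopping rule should not rest on inference. The opposite reading, that an off-ART subject is trivially compliant, is strained. It would also let a subject who was viraemic at entry count as a loss.

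Four further objections stand:
- The documents give no expected number of co-infected subjects and set no minimum, so there may be nobody after the tenth for the change to act on.
- Criterion 11a is narrow and nothing indicates how many would enter by it. Three of ten is an illustration only.
- No target sensitivity is stated, so no stated target is missed. Even undiluted, the rule fires only 26.4% of the time at 10% loss; the small count matters more than one lost place.
- On-ART subjects who are not ARV-compliant also take places without being countable, and the per-protocol definition does not list HIV-drug non-compliance as an exclusion.

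A reader might infer that co-infected subjects are left without HIV protection. The documents do not support that. Section 6.0 (footnote 5) continues HIV evaluations in co-infected subjects after screening, 7.1.3.4 provides for resistance testing at the failure confirmation visit, and 5.8 leaves management of HIV failure to investigators: "Subjects with HIV virologic failure may continue in the study unless there is a requirement for prohibited concomitant medications". None of this depends on the rule. Section 8.2 also lets the Sponsor review accumulating efficacy and safety data during this open-label study.

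**Conclusion.** The mismatch is real on the current text, and its severity is minor. For any loss rate strictly between 0 and 1, each off-ART subject among the ten lowers the chance that the rule fires, until it reaches zero at nine. The size rests wholly on assumed inputs: for one off-ART subject, 26.4% to 22.5% at 10% true loss and 62.4% to 56.4% at 20%.

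The stronger inference, that the rule will in practice fail to detect loss of HIV control, is not supported. It would need off-ART subjects actually among the first ten, further on-ART subjects after the tenth, and a deciding event among those later subjects; the documents establish none of the three. An 11a subject who starts ART during the study could also become countable.

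Only the decision on further co-infected enrolment is affected, so the point has practical force only while that enrolment is open. No primary or secondary endpoint changes.

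**What to change.** In the first bullet of 5.11.3, directly after the reference to the PP population, insert: *enrolled on ART under inclusion criterion 11b*.

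No new data are needed, because ART status is established at entry and HIV RNA is already scheduled for co-infected subjects.

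**Costs**
- The ten may take longer to accrue.
- The false-stop chance returns to that of a true 2-of-10 rule. At an assumed acceptable loss of 5% it is 8.6%, against 7.1% with one of the ten off ART or 4.4% with three.

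**Residual limitation.** ARV-non-compliant subjects can still take places, so the phrase does not guarantee ten subjects at risk. Compliance becomes known only after entry, so it is better to report the number of non-compliant subjects among the ten when the rule is assessed than to build compliance into the count.
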